7.9 Safety Analysis

7.9.1 Adverse Events

All adverse events will be coded using the latest version of MedDRA. In this dictionary, each verbatim term is coded to a lower level term, and then mapped to a preferred MedDRA term, which is then mapped to an SOC. All adverse events from the safety analysis set will be included in the data listings but only treatment-emergent adverse events will be included in the summary tables.

A treatment-emergent adverse event (TEAE) is defined as an adverse event with an onset that occurs after receiving study drug (AE start date \geq first dose date) and within 30 days after receiving the last dose of study drug (AE start date – last dose date \leq 30). Adverse events with onset occurring more than 30 days after last dose of study drug (AE start date – last dose date $>$ 30) will be listed, but not included in the summary tables. Adverse events with missing onset dates will be summarized regardless of severity and relationship to study medication.

Serious adverse events (SAEs) with onset that occurs after receiving study drug (AE start date \geq first dose date) and within 30 days after receiving the last dose of study drug (AE start date - last dose date \leq 30) will be summarized.

In the high-level adverse event summary tables, TEAEs will be summarized regardless of intensity and relationship to study drug. Within each subject, multiple reports of events that map to a common MedDRA term will be counted only once for calculating incidence rates.

At the adverse event level, the summary tables will present the number of subjects reporting each of these MedDRA events, ie, the numbers of subjects reporting 1 or more events that map to the given MedDRA term.

At the SOC level, the summary tables will present the number of subjects reporting 1 or more events that map to the given SOC. That is, the number of subjects reported at the SOC level will be less than or equal to the sum of the subject counts across all adverse events within that SOC.

In selected summaries (TEAEs overview, and TEAEs by SOC and preferred term), adverse events will be summarized by the number of events reported in addition to the number and percentage of subjects with at least one event.

For the summary of TEAEs by SOC, preferred term and maximum intensity, if a subject experiences more than 1 episode of a particular coded adverse event, the subject will be counted only once by the maximum intensity of the episode (preferred term). Similarly, if a subject has more than 1 adverse event within an SOC, the subject will be counted only once by the

maximum intensity in that SOC. Adverse events with missing severity will be classified as having the highest severity.

TEAEs classified in the eCRF as possibly or probably related to the study medication will also be summarized by preferred term and SOC. If a subject experiences more than 1 episode of a particular coded adverse event, the subject will be counted only once by the most related report for the preferred term. Similarly, if a subject has more than 1 adverse event within an SOC, the subject will be counted only once by the most related report in that SOC. Adverse events with missing relationship will be classified as having the highest relationship to study drug.

The following summaries will be presented:

- Overview of TEAEs during the study - number and percentage of subjects, number of events.
- TEAEs by SOC and preferred term - number and percentage of subjects.
- TEAEs by SOC and preferred term by sex (male and female) - number and percentage of subjects.
- TEAEs by SOC and preferred term by age - number and percentage of subjects.
- TEAEs by SOC - number and percentage of subjects.
- TEAEs by preferred term - number and percentage of subjects.
- Intensity of TEAEs by SOC and preferred term - number and percentage of subjects.
- Relationship of TEAEs by SOC and preferred term - number and percentage of subjects.
- Drug-related TEAEs by SOC and preferred term - number and percentage of subjects.
- TEAEs leading to study discontinuation by SOC and preferred term - number and percentage of subjects.
- Treatment-emergent Serious AEs by SOC and preferred term - number and percentage of subjects.
- Most Frequent($\geq 5\%$) Treatment-emergent Non-serious AEs by SOC and preferred term - number and percentage of subjects.
- Pretreatment Events by SOC and preferred term - number and percentage of subjects.

SOCs will be sorted in alphabetical order. Within an SOC, adverse events will be sorted in descending order of total number of subjects with the preferred term.

All adverse events will be presented in listing. Special listings for TEAEs leading to study discontinuation, SAEs and deaths will also be presented.

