10.1.7 Causality of AEs

The relationship of each AE to study drug(s) will be assessed using the following categories:

Related: An AE that follows a reasonable temporal sequence from administration of a drug (including the

course after withdrawal of the drug), or for which possible involvement of the drug cannot be ruled out, although factors other than the drug, such as underlying diseases, complications,

concomitant medications and concurrent treatments, may also be responsible.

Not Related: An AE that does not follow a reasonable temporal sequence from administration of a drug and/or

that can reasonably be explained by other factors, such as underlying diseases, complications,

concomitant medications and concurrent treatments.

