10.1.8 Relationship to Study Procedures

Relationship (causality) to study procedures should be determined for all PTEs and AEs.

The relationship should be assessed as Related if the investigator considers that there is reasonable possibility that an event is due to a study procedure. Otherwise, the relationship should be assessed as Not Related.

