10.2.1.2 PTE and AE Reporting

At each study visit, the investigator will assess whether any subjective AEs have occurred. A neutral question, such as "How have you been feeling since your last visit?" may be asked. Subjects may report AEs occurring at any other time during the study. Subjects experiencing a serious PTE must be monitored until the symptoms subside and any clinically relevant changes in laboratory values have returned to Baseline or there is a satisfactory explanation for the change.

Nonserious PTEs, related or unrelated to the study procedure, need not to be followed-up for the purposes of the protocol.

All subjects experiencing AEs, whether considered associated with the use of the study drug or not, must be monitored until the symptoms subside and any clinically relevant changes in laboratory values have returned to Baseline or until there is a satisfactory explanation for the changes observed. All PTEs and AEs will be documented in the PTE/AE page of the eCRF, whether or not the investigator concludes that the event is related to the drug treatment. The following information will be documented for each event:

- 1. Event term.
- 2. Start and stop date.
- 3. Frequency.
- 4. Intensity.
- 5. Investigator's opinion of the causal relationship between the event and administration of study drug(s) (related or not related) (not completed for PTEs).
- 6. Investigator's opinion of the causal relationship to study procedure(s), including the details of the suspected procedure.
- 7. Action concerning study drug (not applicable for PTEs).
- 8. Outcome of event.
- 9. Seriousness.

All outcomes used in this study will not be used as a primary means to collect AEs. However, should the investigator become aware of a potential AE through the information collected with this instrument, proper follow-up with the subject for medical evaluation should be undertaken. Through this follow-up if it is determined that an AE not previously reported has been identified, normal reporting requirements should be applied.

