13.1.4 Safety Analysis

AEs will be summarized using the safety analysis set. No statistical testing or inferential statistics will be generated.

All AEs will be coded using MedDRA. Data will be summarized using preferred term and primary system organ class.

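### The SAP selects drug-related TEAEs by two causality labels that the Protocol does not collect; the filter should read Related

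*SAP*

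**What the plan says.** SAP 7.9.1 (Adverse Events) gives one selection rule for drug-related events: "TEAEs classified in the eCRF as possibly or probably related to the study medication will also be summarized", by preferred term and system organ class. It then counts each subject once, by the most strongly related report, and assigns an event with missing causality to the strongest relationship level. The list of outputs that follows includes a drug-related TEAE table and, separately, a table of TEAEs by relationship.

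The Protocol sets the scale on which causality is recorded. Section 10.1.7 lists two categories for relationship to study drug, Related and Not Related. Related includes events "for which possible involvement of the drug cannot be ruled out". Section 10.2.1.2 says "All PTEs and AEs will be documented in the PTE/AE page of the eCRF", and among the items recorded for each event it lists the investigator's opinion of the "causal relationship between the event and administration of study drug(s) (related or not related) (not completed for PTEs").

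**The concern.** The SAP filter names values that, on the Protocol's account, no investigator will enter. A graded scale (possibly, probably) has been applied to data collected on a binary one. Neither document defines the graded terms or says how they correspond to Related and Not Related.

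What is at stake is one descriptive safety table. A program that follows the SAP literally would return an empty table, which could be misread as no drug-related events. A program that departs from the SAP would rest on a coding decision that the plan does not document. Safety and tolerability are among the study's stated additional objectives, so the rule that defines drug-related events should be executable as written.

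**Working it through.** No arithmetic formula applies and the plan states no figure on this point. The check compares category labels and then traces which outputs depend on them.

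**Step 1. Compare the categories.**

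| Source | Item | Categories |
|---|---|---|
| Protocol 10.1.7 and 10.2.1.2 | Relationship to study drug | Related; Not Related |
| Protocol 10.1.8 | Relationship to study procedures | Related; Not Related |
| SAP 7.9.1 | Filter for drug-related TEAEs | possibly related; probably related |

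Of the 2 SAP filter values, 0 match a Protocol category. The procedure-causality item does not supply the missing labels either. It too has two levels, and its rule ends "Otherwise, the relationship should be assessed as Not Related".

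**Step 2. Look for a mapping.** Neither document contains one. SAP 7.11, the section for changes to the plan, is an unfilled placeholder, so it records no change of scale.

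**Step 3. Apply the filter literally.**
- Event recorded as Related: not selected.
- Event recorded as Not Related: not selected.
- Event with missing relationship: the SAP's rule moves it to the strongest level, which on the Protocol scale is Related. It is still not selected.

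**Step 4. Apply the filter with Related in place of the two labels.** Every event recorded as Related is selected. Events with a missing relationship are selected too, under the SAP's own rule.

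**Step 5. Count the outputs that depend on it.** SAP 7.9.1 lists 13 summaries: 1 + 1 + 11 = 13.
- 1 is affected by inference, the drug-related TEAE table. The SAP gives no other definition of drug-related.
- 1 is unknown, listed as "Overview of TEAEs during the study - number and percentage of subjects, number of events". Its rows are not specified, so it may or may not carry a related-TEAE row.
- 11 have no drug-related restriction in their titles: SOC and preferred term; by sex; by age; by SOC; by preferred term; intensity; relationship; leading to discontinuation; serious; most frequent non-serious; pretreatment events. The last of these could not use the filter in any case, because drug causality is not completed for pretreatment events.

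**The case against.** The strongest reply is that this is outdated wording with almost no practical consequence. The Protocol's definition of Related already covers possible involvement of the drug, so the SAP phrase reads as an older name for the same set. With only two recorded values, a programmer has one plausible reading, and an empty table is unlikely in practice. Nothing is lost even on the literal reading, because the Relationship table and the full AE listing show the Related events. Protocol 13.1.4 also says of safety: "No statistical testing or inferential statistics will be generated". These points stand, and they are why the matter is minor. They do not make the rule correct: a reading that every programmer is expected to substitute belongs in the text.

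A second reply is that the SAP sentence points to the eCRF, which is not among the documents and might carry a graded scale. The Handling Rules for Analysis Data, also not available, could in principle address it. This limits what can be said about the actual data. It does not remove the conflict, because Protocol 10.2.1.2 states what is recorded for each event. A graded eCRF would itself depart from the Protocol and would need reconciling.

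A third reply is that including the Overview is speculative, since the SAP says "In the high-level adverse event summary tables, TEAEs will be summarized regardless of intensity and relationship to study drug". That is fair: no related-TEAE row is specified there, and the Overview is counted as unknown, not affected. It is also true that the existing missing-relationship rule already gives Related on a two-level scale, so restating it is a clarification only.

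**Conclusion.** The concern holds. The SAP's rule for selecting drug-related TEAEs is wrong as written, because neither of its 2 filter values is a category the Protocol collects. Severity is minor. One descriptive table is affected by inference, one is uncertain, and 11 of the 13 state no drug-related restriction. No effectiveness estimate or denominator changes.

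Two assumptions carry this conclusion. The first is that the eCRF follows the Protocol's two-level scale. The second is that the quoted sentence governs the drug-related TEAE table, which the SAP implies but does not state. Confidence is high for the conflict between the two documents. What a program would actually produce depends on the unseen eCRF and on how the programmer reads the sentence.

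**What to change.** In SAP 7.9.1:

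- Replace the two graded labels with Related, as defined in Protocol 10.1.7.
- State that this defines the drug-related TEAE table and any related-TEAE row in the Overview.
- State that a TEAE with missing relationship is counted as Related. The phrases about the most related report and the highest relationship then have a plain meaning on a two-level scale: Related ranks over Not Related.

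Before the change is made, the category labels should be confirmed against the eCRF. The cost is a one-sentence wording change to the SAP, with no change to data collection.

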7.9.2 Vital Signs and Weight

Vital signs and weight at scheduled visits and their changes from Baseline will be summarized using descriptive statistics by visit and end of study. The number and percentage of subjects with

at least one post-Baseline MAV from vital signs during the treatment period will be presented for each variable over all visits. A listing of MAVs for vital signs will also be presented.

The criteria for identification of MAV vital signs are given in Appendix A.

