Urine drug screen test kits will be supplied by the sponsor for UDS testing at the clinic. Urine for drug screening will not be sent to the central laboratory for testing. The central laboratory will perform laboratory tests for serum pregnancy, hematology and limited serum chemistries. Local UDS and urine pregnancy screening results must be confirmed prior to conducting the Baseline Visit. Serum pregnancy collected at Baseline should be sent to the central laboratory. In the case of a combined Screening and Baseline Visit the UDS and the urine pregnancy test will be done once

in the clinic and a serum pregnancy test will be sent to the central laboratory. The results of central laboratory tests will be returned to the investigator, who is responsible for reviewing and filing these results.

If subjects experience ALT or AST >3 ×ULN, follow-up laboratory tests (at a minimum, serum alkaline phosphatase, ALT, AST, total bilirubin, gamma-glutamyl transferase, and INR) should be performed within a maximum of 7 days and preferably within 48 to 72 hours after the abnormality

was noted. (Refer to Section 7.4 and Section 10.2.3 for the appropriate guidance on reporting abnormal liver function tests.)

If ALT or AST remains elevated >3×ULN on these 2 consecutive occasions, the investigator must contact the Medical Monitor for consideration of additional testing, close monitoring, possible discontinuation of sponsor-supplied drug. discussion of the relevant subject details and possible alternative etiologies. The abnormality should be recorded as an AE (please refer to Section 10.2.3).

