10.1.3 Additional Points to Consider for PTEs and AEs

An untoward finding generally may:

- Indicate a new diagnosis or unexpected worsening of a pre-existing condition. (Intermittent events for pre-existing conditions or underlying disease should not be considered PTEs or AEs.)
- Necessitate therapeutic intervention.
- Require an invasive diagnostic procedure.
- Require discontinuation or a change in dose of study drug or a concomitant medication.
- Be considered unfavorable by the investigator for any reason.
- PTEs/AEs caused by a study procedure (eg, a bruise after blood draw) should be recorded as a PTE/AE eCRF page.

Diagnoses vs signs and symptoms:

• Each event should be recorded to represent a single diagnosis. Accompanying signs (including abnormal laboratory values or electrocardiogram [ECG] findings) or symptoms should NOT be recorded as additional AEs. If a diagnosis is unknown, sign(s) or symptom(s) should be recorded appropriately as a PTE(s) or as an AE(s).

Laboratory values and ECG findings:

• Changes in laboratory values or ECG findings are only considered to be PTEs or AEs if they are judged to be clinically significant (ie, if some action or intervention is required or if the investigator judges the change to be beyond the range of normal physiologic fluctuation). A

- laboratory or ECG re-test and/or continued monitoring of an abnormal value or finding are not considered an intervention. In addition, repeated or additional noninvasive testing for verification, evaluation or monitoring of an abnormality is not considered an intervention.
- If abnormal laboratory values or ECG findings are the result of pathology for which there is an overall diagnosis (eg, increased creatinine in renal failure), the diagnosis only should be reported appropriately as a PTE or as an AE.

Pre-existing conditions:

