10.1.5.2 Liver Injury

Management of liver toxicity AEs is described in Section 7.4 of the protocol. If ALT or AST >3×ULN, laboratory tests should be repeated within a maximum of 7 days, and preferably within 48 to 72 hours. If the ALT or AST remains elevated >3×ULN on these 2 consecutive occasions, and this observation cannot be explained by concomitant disease or another alternative causality, the abnormality should be recorded on an AE page. The investigator must contact the Medical Monitor for consideration of immediate discontinuation of study drug, discussion of the relevant subject details and possible alternative causalities.

If a subject is noted to have an ALT or AST >3×ULN and total bilirubin >2×ULN for which an alternative etiology has not been identified, the event should be recorded as an SAE and reported as per Section 10.3.1. In addition, an LFT increases eCRF must be completed and transmitted with the SAE

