10.2.3 Reporting of Abnormal LFTs

If a subject is noted to have ALT or AST elevated >3×ULN on 2 consecutive occasions, the abnormality should be recorded as an AE. In addition, an LFT Increases eCRF must be completed providing additional information on relevant recent history, risk factors, clinical signs and symptoms and results of any additional diagnostic tests performed.

If a subject is noted to have ALT or AST >3×ULN and total bilirubin >2×ULN for which an alternative etiology has not been identified, the event should be recorded as an SAE and reported as per Section 10.2.2. The investigator must contact the Medical Monitor for discussion of the relevant subject details and possible alternative etiologies, such as acute viral hepatitis A or B or other acute liver disease or medical history/concurrent medical conditions. Follow-up laboratory

tests as described in Section 9.1.8 must also be performed. In addition, an LFT Increases eCRF must be completed and transmitted with the Takeda SAE form (as per Section 10.2.2).

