Appendix A Schedule of Study Procedures

	Screening	Treatment						
	Visit 1 (a)	Baseline Visit 2 (a) Day 1	Visit 3 Wk 2	Telephone Contact Visit 4 Wk 4	Visit 5 Wk 6	Telephone Contact Visit 6 Wk 9	End of Study Visit 7 Wk 12 /Early Termination	Visit 8 Wk 16
	Days -21 up to -1	Day 1	Day 15 (±3 Days)	Day 29 (±3 Days)	Day 43 (±5 Days)	Day 64 (±5 Days)	Day 85 (±5 Days)	Day 113 (± 7 Days)
Informed consent	X							
Eligibility criteria	X	X						
Demographics, medical history, medication history	X							
UDS (b)	X	X						
MDD diagnosis confirmed by investigator judgment, antidepressant medication history & disease history	X							
Height and weight (c)	X	X					X	
Hematology and limited serum chemistry		X					X	
PGx sample collection (d)		X					X	
Concurrent medical conditions	X	X						
Concomitant medications		X	X	X	X	X	X	X
Vital signs	X							
GAS assessment		X			X		X	
PHQ-9	X	X			X		X	
Q-LES-Q		X					X	
PDQ-D		X			X		X	
Company Confidential Inform	ation							
Company Confidential Inforn								
Company Confidential Inforn	nation							
C-SSRS	X	X	X		X		X	
Company Confidential Inforn	nation							
WHO-5		X			X		X	
CGI-S	X	X	X		X		X	
CGI-I			X		X		X	

Footnotes are on last table page.

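### Protocol sections disagree on whether a symptom-free study-drug overdose is an AE, and SAP 7.9 plans no output for the liver chemistry the trial collects

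*SAP*

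**What the plan says.** **Collection.** Protocol Appendix A schedules "Hematology and limited serum chemistry" at Baseline and at Week 12/Early Termination. Table 9.a puts ALT, AST and total bilirubin in that panel, and 9.1.8 has the central laboratory run it.

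**Reporting.** SAP 7.9 covers AEs (7.9.1), vital signs and weight (7.9.2) and the C-SSRS (7.9.3). For AEs, "only treatment-emergent adverse events will be included in the summary tables". For measurements, "Vital signs and weight at scheduled visits and their changes from Baseline will be summarized using descriptive statistics by visit and end of study". SAP Appendix A sets abnormal-value limits for blood pressure, pulse and weight only.

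**Liver rules.** After ALT or AST above 3×ULN, Protocol 9.1.8 says follow-up tests "should be performed within a maximum of 7 days and preferably within 48 to 72 hours after the abnormality" was noted. Section 10.2.3 says: "If a subject is noted to have ALT or AST elevated >3×ULN on 2 consecutive occasions, the abnormality should be recorded as an AE". Section 9.1.8 gives the same instruction. Section 10.1.5.2 adds a condition for the confirmed case: if "this observation cannot be explained by concomitant disease or another alternative causality, the abnormality should be recorded on an AE page". More generally, 10.1.3 says: "Changes in laboratory values or ECG findings are only considered to be PTEs or AEs if they are judged to be clinically significant".

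**Overdose rules.** Protocol 10.1.3 excludes an overdose of any medication from AE status when it produces no side effects, and sends it to the Overdose page of the eCRF. Section 10.1.5.3 has every overdose documented as an AE. Section 10.2.1.3 requires AEs of special interest, which include overdose, to be entered as AEs. Section 8.1.4 sends all overdoses to the Overdose page and only accompanying events to the AE page.

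**The concern.** Assessing safety and tolerability is a stated additional objective. Liver injury and overdose are two of the three AEs of special interest.

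On overdose, the same symptom-free case is an AE under one section and not under another, and no section says which prevails. With about 25 sites, the AE count can depend on which page a site reads.

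On liver chemistry, Week 12/Early Termination is the only scheduled post-dose draw. As planned, its results reach the report only when an investigator records an AE. The report could not state how many subjects crossed a given ALT or AST multiple.

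**Working it through.** There is no planned figure to reproduce. The check sets the sections side by side and adds some short arithmetic.

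**1. Overdose: a study-drug overdose with no symptoms**

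| Section | Overdose page | AE page |
|---|---|---|
| 8.1.4 | yes | only for associated events, so no |
| 10.1.3 | yes | no |
| 10.1.5.3 | overdose form | yes |
| 10.2.1.3 | specific form | yes |

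A site cannot obey both 10.1.3 and 10.1.5.3. The Overdose form is required either way, so what varies is the AE label.

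Size, assuming all 120 planned subjects are dosed and so enter the Safety Analysis Set:
- 1 discordant case: 1/120 = 0.83 percentage points.
- 3 discordant cases: 3/120 = 2.5 points.

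This applies to the overdose row. The any-TEAE row moves only if the subject has no other TEAE. The documents give no overdose rate, so 1 and 3 are illustrations.

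**2. Liver chemistry: where each result goes**

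| Finding | Planned output |
|---|---|
| ALT/AST >3×ULN with bilirubin >2×ULN, no other cause found | SAE tables and listing (10.1.5.2, 10.2.3) |
| ALT/AST >3×ULN confirmed, unexplained | AE tables (9.1.8, 10.1.5.2, 10.2.3) |
| ALT/AST >3×ULN confirmed, explained | AE under 9.1.8 and 10.2.3; 10.1.5.2 does not call for it |
| ALT/AST >3×ULN not confirmed, not judged clinically significant | none |
| Any lower elevation not judged clinically significant | none |

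None of the 13 summaries in SAP 7.9.1 tabulates a laboratory value; they count coded events, including any liver event recorded as an AE. None of the 4 criteria in SAP Appendix A is a laboratory criterion.

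Amount of data without an output:
- Low end, 120 Baseline draws plus 100 completers at Week 12: 120 + 100 = 220 draws.
- High end, all 20 non-completers also drawn at Early Termination: 120 + 120 = 240 draws.
- For ALT, AST and total bilirubin: 220 × 3 = 660 to 240 × 3 = 720 results.

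**3. Closest-date rule**

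SAP 7.1.2 keeps one value per window, the one nearest the scheduled day, with window bounds midway between visits. Week 12 is Day 85 and the next contact is Day 113, so the upper bound is (85 + 113)/2 = Day 99. A draw on Day 85 with a repeat 7 days later, on Day 92, falls in one window. The Day 85 value is kept and a higher Day 92 value is dropped. A count based on the highest value therefore has to be exempt from this rule.

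**4. Liver wording**

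Section 10.1.5.2 says when a confirmed elevation is recorded. It does not say that an explained one must not be. A site that records every confirmed elevation satisfies 9.1.8, 10.2.3 and 10.1.5.2 together. Where the cause is a known diagnosis, however, 10.1.3 has the diagnosis reported and not the laboratory value, which sits awkwardly with 9.1.8 and 10.2.3.

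**The case against.** The strongest reply is that nothing promised is missing. Protocol 5.3, Protocol 13.1.4 and SAP 5.4 all leave laboratory tests out of the safety assessments or analyses they name. This stands: a reader might infer that the SAP departs from the protocol, and it does not. SAP 7.9.2 does plan post-Baseline vital-sign summaries, although Protocol 9.1.4 schedules vital signs only at Screening. That shows uneven planning but creates no duty to tabulate chemistry.

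Second, a reader might infer that serious liver cases would go unseen. They would not. Confirmed elevations should become AEs, and the unexplained combined ALT/AST and bilirubin case is an SAE without a repeat. Subjects stopped under Protocol 7.4 appear in disposition and in the tables of TEAEs leading to discontinuation. That last route is narrow, because the only scheduled post-dose draw for a completer comes at the end of treatment.

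Third, a reader might see 10.1.5.2 as flatly contradicting 9.1.8 and 10.2.3. It gives a sufficient condition, so this is loose drafting. An explained elevation may also already be counted through its diagnosis, so no percentage-point effect is claimed for it.

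Fourth, no overdose is lost, because every rule requires a form. True, but the planned tables count AEs, and the AE label is what the sections dispute.

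**Conclusion.** This is a cheap improvement worth making. It does not touch the primary endpoint or any planned inference.

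- **Overdose:** a genuine contradiction in current protocol text, worth 0.8 points on the overdose row per discordant case if 120 subjects are dosed. That identical cases would be recorded differently is an inference from the conflicting instructions; the protocol does not grant sites that discretion in words.
- **Liver chemistry:** a real gap limited to elevations that are unconfirmed, or explained and not judged clinically significant. The documents give no elevation rate, so the number of affected subjects is unknown.
- **Liver wording:** minor.

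A reader might expect the added counts to show who met the Protocol 7.4 stopping limits. They would not do so fully: 7.4 also uses persistence beyond 2 weeks, INR, and symptoms or eosinophilia. Nor do the documents show that every unscheduled repeat enters the database, so only the scheduled results can be taken as available.

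**What to change.** **1. Overdose (protocol).** In 10.1.3 add: *except overdose of study drug, see 10.1.5.3*. In 8.1.4 add that a study-drug overdose is also recorded on the AE page. Without the second edit the inconsistency survives.

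**2. Liver chemistry (SAP 7.9).** On the Safety Analysis Set, descriptive only, in keeping with Protocol 13.1.4:
- ALT, AST and total bilirubin at Baseline and Week 12/Early Termination, with change.
- A shift table from Baseline to the highest post-dose value, so that elevations present at entry are visible.
- Number and percentage of subjects with ALT/AST >3, >5 or >8×ULN, or >3×ULN with total bilirubin >2×ULN.

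Use scheduled values plus any unscheduled values held in the database, and exempt the highest-value table and the counts from the SAP 7.1.2 closest-date rule. Footnote that these are numeric thresholds only and omit the persistence, INR and symptom parts of 7.4.

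**3. Liver wording (protocol, minor).** Align 10.1.5.2 with 9.1.8 and 10.2.3 for explained, confirmed elevations. State in all three that a known diagnosis is reported in place of the laboratory value, as 10.1.3 requires. Simply deleting the condition in 10.1.5.2 would leave all three at odds with 10.1.3.

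**Cost.** A little programming, no new test or visit, protocol wording changes that need IRB approval (Appendix B, item 5), and possibly a few more recorded AEs.
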